6.1.3.1 Model checking procedures

The analyses of residuals will be performed to assess model assumptions.

6.1.3.2 Sensitivity analysis

Missing not at random (MNAR) analysis

Given the severity of disease and the likelihood of some missing data, the analysis will also include approaches to assess treatment under the assumption of missing not at random (MNAR). Missing data will be imputed using methods specific to non-monotone and monotone missing patterns. In a first step, non-monotone missing data will be imputed 1000 times using MCMC method. Then monotone missing data will be imputed by pattern-mixture model (MNAR) performed on the 1000 samples (O'Kelly & Ratitch 2014). A conservative analysis where missing values in the active group are imputed based on the behavior observed in the placebo group (unconditional reference approach) will be used. The objective is to assess if a potential effect observed in the analysis based on MAR assumption is still present when a more conservative procedure is used. The detail of the sensitivity analyses is described in the appendix 2 (section 10.2).

Analysis of potential Covid-19 impact

As primary analysis may exclude some data due to Covid-19, a sensitivity analysis will also include all PD data regardless of protocol deviations linked to Covid-19.

Covid-19 may interfere with study outcomes due to the following:

- Missing visits with missing FVC assessment and/or missing treatment doses due to restriction in travel or closed site. These missing data are considered as missing completely at random therefore introducing no systematic bias in treatment effect.
- Missing visits due to adverse event linked to Covid-19
- Infection by Covid-19.
- Alteration in recruitment after the start of pandemic as some patients might want to avoid participation in the study due to the Covid-19 risk.

The date of when Covid-19 occurred in different countries is tabulated below. Any patient data collected after that date may be confounded by complications due to the pandemic. For example, if a patient has any on-treatment observation collected after the start date for the specific region, that patient's estimated treatment effect is considered potentially affected by the pandemic.

Table 6-1 COVID-19 date

Region/Country	Start Date	End Date
China	01-Jan-2020	End date has not yet been defined
South Korea	20-Feb-2020	End date has not yet been defined
Japan	21-Feb-2020	End date has not yet been defined
Italy	23-Feb-2020	End date has not yet been defined
Rest of the World	01-Mar-2020	End dates have not yet been defined

If sufficient data is present the interaction of covid-19 by treatment will be assessed by means of descriptive statistics:

- Demographics of patients recruited pre- and during COVID period by treatment and for all
- Number of patients with missed visits pre- and during COVID period overall and by treatment and for all
- Adverse events pre- and during COVID period by treatment and for all
- Boxplots of FVC change from baseline pre- and during COVID period by treatment and for all

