6.1.3 Statistical model, assumptions and hypotheses

The following hypothesis will be tested for VAY736+SoC versus Placebo+SoC:

H0: There is no difference or worsening in change from baseline in FVC (L) from baseline to 48 weeks of treatment between VAY736+SoC and placebo+SoC

H1: There is an improvement in change from baseline in FVC (L) from baseline to 48 weeks of treatment between VAY736+SoC and placebo+SoC

Test will be conducted at a one-sided 10% level and 2-sided 80% CI of the estimates will be displayed. Sense of the one-sided test for each criteria is given in table of appendix 1 (section 10.1).

The primary variable, change from baseline in FVC (L) will be analyzed using a Mixed Effects Model for Repeated Measures (MMRM) in the PD analysis set and considering all assessments collected during the treatment epoch. The model will include treatment and visit as fixed effects, standard of care treatment (Nintedanib, Pirofendone, or no treatment) as factor and baseline value as a covariate, treatment-by-visit and baseline-by-visit as interaction terms. The within subject correlation will be modeled using a repeated statement in SAS Proc Mixed with unstructured covariance matrix. In case of non convergence the model, an alternative AR(1) covariance may be implemented. The posterior will be derived as a t-distribution using a PROC MIXED as detailed in section 3. The main comparison will be a contrast between treatment groups at 48 weeks of treatment. This approach assumes data is Missing At Random (MAR).

Commercially Confidential Information

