Values of the MCMC parameters NBITER (the number of MCMC updates allowed for the sampler to converge to the posterior distribution, and NITER (the number of iterations between each saved draw from the posterior) may need to be increased to allow the MCMC estimates stabilize.

Assumptions underlying this partial imputation step would be of the MAR type, i.e., that subjects with intermediate missing data follow the same model as other subjects in their respective treatment arm that continue the study. This is a reasonable assumption for this partial imputation process because subjects tend to miss intermediate visits due to scheduling conflicts or other reasons generally unrelated to their medical condition under study.

If the proportion of non-monotone missing data is small compared to the number of subjects that discontinue from the study permanently, imputing these few non-monotone values using the partial MCMC method under MAR assumptions would have a small impact on the overall analyses. Note that we will use 1000 imputations. This number is much larger than the default in most software packages. This high number of imputations decrease at the best the uncertainty of the imputation and using as many as 1000 or so imputations does not present any computational difficulties with the current technology.

The output data set DIN_MONO from the above call to PROC MI can now be used as input to a subsequent call of PROC MI to impute the remaining monotone missing values. Since dataset DIN_MONO already contains 1000 copies of the data with partial imputations, the subsequent call to PROC MI will use a BY _Imputation_ statement and request one imputed dataset (n_impute=1 option) within each BY group. This second call will be based on a Not Missing At Random (NMAR) approach as described in B part.

B- NMAR data imputation

Reference-based pattern imputation (unconditional reference)

Assuming that non-monotone missing data have already been imputed using the MCMC method as described above we will then break the imputation process into a sequence of MIs, where each MI is intended to impute missing values at one time-point only, as follows.

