- i. In order to impute missing data at time-point 1 (W5) and based on the definition of the link function, first prepare an input dataset, making sure that it will contain only the intended donor pattern (P1: control subjects with non-missing values) and recipient patterns (P2: control arms with missing data and P4 active group with missing data). Separate the input dataset DIN_MONO into two datasets: DIN_MONO_IMP1, containing all control subjects and those subjects from the active group that have values at W4 missing (patterns P1, P2 and P4); and DIN_MONO_REST1, containing the subjects from the active group with non-missing values (pattern P4).

```
data DIN_MONO_IMP1  DIN_MONO_REST1;
  set DIN_MONO;
  *** subjects from the VAY736 non-missing values at W5 ***;
  if DRUGNUM=1 and LASTVIS>=5 then output DIN_MONO_REST1;
  ***All other included VAY736 with missing W5 ***;
  else output DIN_MONO_IMP1;
run;
```

- i. Call PROC MI to impute missing data at time-point 1 using dataset DIN_MONO_IMP1 as input.

```
proc mi data= DIN_MONO_IMP1 out= DIN_REG_IMP1 nimpute=1  
seed=234;  
  by _Imputation_;  
  var SOC_TYPE BASE W5;  
  monotone regression (W5 = SOC_TYPE BASE);  
run;
```

Note that treatment arm is not included as an effect in the model (it is not included in the VAR statement). Since subjects from the active group with non-missing values at time-point t are not included in the input dataset, they will not contribute to the estimation of an imputation model for time-point t. The imputation model will be estimated using control subjects only, while this call to PROC MI will impute missing data at time-point t for all subjects who need imputation at that time-point. This way, subjects from active group will be imputed based on the control subjects' model.

- ii. Assemble a dataset containing all subjects while including the just-imputed visit t data so that they can serve as predictors for the imputation of the next visit.

```
data DIN_IMP1;  
  set DIN_REST1 DIN_REG_IMP1;  
run;
```

- iii. Repeat steps (i)-(iii) for all other time-points sequentially using a reconstructed dataset (e.g., DIN_IMP1) as a starting point in step (i).

C- Modelling on M complete datasets

Once all missing data has been imputed then an ANCOVA of the change from baseline of FVC (CHANGE) at week 49 visit will be applied by _Imputation_ as per model below:

```
proc mixed data=DIN_FULLIMP;  
  by _Imputation_;  
  where VISIT='Week 49'  
  class DRGNUM SOC_TYPE;  

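### The missing-not-at-random check labelled unconditional reference is specified as a conditional (copy-reference type) imputation, so it is milder than its label implies

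*SAP*

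**What the plan says.** SAP 6.1.3.2 plans a conservative analysis in which "missing values in the active group are imputed based on the behavior observed in the placebo group (unconditional reference approach"). The purpose is to see whether an effect found under MAR "is still present when a more conservative procedure is used". The section sends the reader to Appendix 2 for the detail.

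Appendix 2, part B, repeats the label in its subheading, "Reference-based pattern imputation (unconditional reference"), and then gives the algorithm:

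- At each visit the VAY736 patients with an observed value are set aside, so that "The imputation model will be estimated using control subjects only".
- The one model line printed is for the first visit: "monotone regression (W5 = SOC_TYPE BASE").
- All patients are then put back together, "including the just-imputed visit t data so that they can serve as predictors for the imputation of the next visit".
- The cycle continues: "Repeat steps (i)-(iii) for all other time-points sequentially using a reconstructed dataset".

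The completed data are analysed by ANCOVA at Week 49 and pooled by Rubin's rules.

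**The concern.** An imputation that is unconditional on the drop-out's own course gives a departing VAY736 patient a placebo-like outcome and no credit for FVC preserved before leaving. The algorithm does something else. Once a VAY736 patient has post-baseline FVC, those values sit in the reassembled dataset and drive the prediction of the next visit. Placebo coefficients applied to a history shifted by benefit pass part of that shift on to Week 49. This is imputation conditional on own history, the copy-reference type. The two methods agree only for patients who leave before any post-baseline FVC.

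At stake is what the check can claim. With 29 patients per arm and serious disease, some missing FVC is expected. A report that the effect survived an unconditional-reference analysis would describe a harsher test than the one specified.

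**Working it through.** **1. Label against algorithm.** The printed first-visit model uses standard of care and baseline only, but no post-baseline value exists at that point, so it cannot tell the two methods apart. The later models are not printed. The sentence about predictors for the next visit settles how they work. Nothing in the appendix resets a VAY736 drop-out's mean to the placebo mean. (The appendix steps through four-weekly visits from Week 5, while Protocol 3.1 schedules efficacy assessments at Weeks 1, 13, 25, 37 and 49. The first scheduled FVC to impute is therefore Week 13.)

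**2. The plan's own figure.** Protocol 11.7: 58 patients 1:1, SD 250 ml, effect 160 ml, at least 80% power. The test is one-sided at 10%.

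- SE = 250 × √(2/29) = 65.7 ml.
- Power = Φ(160/65.7 − 1.282) = Φ(1.155) = 87.6%, consistent with the statement.

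The documents give no figure for the sensitivity analysis itself.

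**3. Inputs for the comparison.** From the documents: 160 ml, 250 ml, quarterly visits, and the 20% threshold in Protocol 11.7, used here only as a scenario for missing Week 49 FVC. Assumed, because the documents give nothing: linear accrual (40, 80, 120, 160 ml at Weeks 13, 25, 37, 49), the within-patient covariance, and the timing of drop-out.

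**4. Formulas.** With S the covariance of the FVC values (or of the changes from baseline):

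- Benefit carried to Week 49 = S[49, observed] × S[observed, observed]⁻¹ × effect[observed].
- Expected contrast at missing fraction d = 160 × (1 − d) + d × mean benefit carried.
- An imputation that ignores own post-baseline values carries 0, so at d = 0.20 the contrast is 160 × 0.8 = **128 ml**.

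**5. Hand check.** If changes from baseline have equal variance and correlation ρ, each of k observed visits has coefficient ρ/(1 + (k − 1)ρ). With ρ = 0.5:

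- Last seen Week 13: 0.5 × 40 = 20 ml.
- Last seen Week 25: 0.333 × (40 + 80) = 40 ml.
- Last seen Week 37: 0.25 × (40 + 80 + 120) = 60 ml.

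The mean is 40 ml, so the contrast is 128 + 0.2 × 40 = 136 ml.

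**6. Structures on the change from baseline, 20% missing, drop-out spread evenly over the last visits shown.**

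| Structure | Carried if last seen W13 / W25 / W37 (ml) | Contrast (ml) | Contrast if a quarter of drop-outs leave before W13 (ml) |
|---|---|---|---|
| Correlation 0.3 | 12 / 28 / 45 | 133.6 | 132.2 |
| Correlation 0.5 | 20 / 40 / 60 | 136.0 | 134.0 |
| AR(1) 0.9 per visit | 29 / 65 / 108 | 141.5 | 138.1 |
| Random walk | 40 / 80 / 120 | 144.0 | 140.0 |
| Random slope plus noise | 48 / 100 / 131 | 146.6 | 142.0 |

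**7. Structures on FVC itself.** Between-patient SD 700 ml, measurement SD 50 to 120 ml, random slope or random walk, SD of the 48-week change held at 250 ml. Drop-outs last seen at baseline, W13, W25 or W37 are split 25% each or 10/20/30/40%.

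- Lowest: random walk, measurement SD 120, carries 0 / 24 / 55 / 89 ml. Even split: 128 + 0.2 × 42 = 136.4 ml.
- Highest: random slope, measurement SD 50, carries 0 / 79 / 129 / 148 ml. Late split: 128 + 0.2 × 113.7 = 150.7 ml.

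**8. Range.** Steps 6 and 7 together give about 132 to 151 ml as coded against 128 ml, a gap of about 4 to 23 ml. The gap is proportional to d: about 2 to 11 ml at 10% missing and 6 to 34 ml at 30%.

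**9. Chance of passing.** Simulation with 29 per arm, 20% missing, 400 trials and 15 imputations gave these chances of one-sided p < 0.10:

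- Random walk: 80% as coded, 70% unconditional.
- Correlation 0.5: 71% as coded, 66% unconditional.

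The Monte Carlo error of each figure is about √(0.7 × 0.3/400) = 2.3 points.

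**10. Early benefit.** If the full 160 ml is present by Week 13 and every drop-out has a post-baseline FVC, the coded contrast is 142 to 170 ml at 20% missing. It is exactly 160 ml under a random walk, where the check removes nothing, and above 160 ml under a random slope.

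**The case against.** The SAP never says what the reference is unconditional on. Its only explanation is that active-arm values follow placebo behaviour, and a model estimated from controls alone does that in one sense. Since the text defers to Appendix 2, the algorithm can be read as the specification and the label as loose wording. This stands in part. A reader might infer that a promised analysis was dropped, and the documents do not go that far. They show a label and an algorithm that do not fit, and the label is what would be reported.

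A reader might also infer that the check is not conservative, or that drop-outs keep most of their benefit. Neither is established. With linear accrual every contrast above is below 160 ml, so the stated aim of being harsher than MAR is met. The share of benefit held at drop-out that is carried runs from about 30% at correlation 0.3 to all of it, or more, under a random walk or random slope. The documents fix none of these assumptions.

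The 20% in Protocol 11.7 concerns patients not completing treatment, not missing Week 49 FVC. Protocol 7.2 asks that patients who stop drug continue to be followed and encourages them to complete spirometry visits. Actual missingness may therefore be lower, and some of the predictor values would be off-drug. This stands and shrinks the gap.

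The gap is also small against sampling error: 4 to 23 ml is 0.06 to 0.35 of the 65.7 ml SE, in a non-gating analysis of an exploratory trial. Finally, redacted text follows both SAP 6.1.3 and Appendix 2, so other MNAR analyses may exist. This is the only one visible.

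**Conclusion.** The point holds as a mismatch between label and method. For any VAY736 drop-out with post-baseline FVC, the specified imputation is conditional on that patient's own history and passes on part of the benefit reached. At 20% missing Week 49 FVC and linear accrual, the expected contrast is about 4 to 23 ml above the 128 ml of an unconditional imputation. The simulated chance of passing is 5 to 10 points higher in the two structures tried. These sizes rest on assumed covariance, effect course, drop-out timing and missing fraction; the direction does not depend on them so long as benefit exists before drop-out and FVC is positively correlated over time. The check is weaker than labelled, not useless, and the primary MMRM is unaffected. It is worth correcting because it changes what the report may say about robustness.

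**What to change.** 1. In SAP 6.1.3.2 and Appendix 2 part B, relabel the existing code as conditional (copy reference), and print the predictors for every visit at which FVC is scheduled.
2. Add one run in which VAY736 recipients' visits after drop-out are imputed from the placebo model without their own post-baseline values. Either use standard of care and baseline only, or use jump to reference. With the latter, the arm difference removed from earlier values must be drawn afresh for each imputation, otherwise its uncertainty is not propagated.
3. Report the two runs side by side as a bracket. Neither needs to be called the main version: the documents do not show which post-drop-out course is more plausible.

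Cost: a wording change and one extra run of an existing program. The downside is a somewhat conservative standard error under Rubin's rules for the added run.

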6.1.3.3 Graphical presentation of results

Plot of model estimates of mean change from baseline and their standard error will be presented over the treatment epoch.

Plot of observed mean change from baseline and their standard error will be presented over the whole study period i.e. double-blind period CCI

6.2 Secondary objectives

6.2.1 Variables

6.2.1.1 Survival (all-cause mortality and IPF-related mortality)

Only events restricted to treatment epoch will be analyzed.

Survival all-cause mortality (S1) is defined as time from randomization to death due to any cause.

Survival IPF related mortality (S2) is defined as time from randomization to death due to IPF related cause.

IPF-related death will be assessed by an Adjudication Committee.

Survival time will be derived in days as follows:

$$(\text{date of death or censoring date} - \text{date of randomization}) + 1$$

For S1, if a patient is not known to have died (all-cause mortality) at the end of the treatment epoch, survival time will be censored at the latest date in treatment epoch where the patient was known to be alive.

For S2, if a patient is not known to have died due to IPF related cause at the end of the treatment epoch, survival time will be censored at the latest date in treatment epoch where the patient was known to be alive or died due to non-IPF related cause.

6.2.1.2 Progression-free Survival

Only events restricted to treatment epoch will be analyzed.

Progression free survival (PFS) is defined as follows:

- PFS1: time from randomization to progression (relative reduction in FVC $\geq 10\%$) or death due to all causes
- PFS2: time from randomization to progression (relative reduction in FVC $\geq 10\%$) or death due to IPF related causes

For PFS1, if a subject has not progressed nor died at the end of the treatment epoch, PFS will be censored at the date of last non-missing assessment of FVC

For PFS2, if a subject has not progressed nor died (IPF related mortality) at the end of the treatment epoch, PFS will be censored at the maximum date of (the last non-missing assessment of FVC during treatment epoch and the non-IPF related death).

6.2.1.3 Disease Progression

Only events restricted to treatment epoch will be analyzed.

Disease progression is defined as the time from randomization to progression.

The following progression events will be considered:

- Progression, defined as: relative reduction in FVC $\geq 10\%$;

- Progression, defined as: relative reduction in DLCO $\geq 15\%$;
- Progression, defined as: absolute reduction in 6MWD ≥ 50 m.

For the subjects who have not progressed at the end of the treatment epoch, disease progression will be censored at the date of the last FVC, DLCO or 6MWD assessment in treatment epoch as applicable.

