11.5 Analysis of secondary variable(s)

11.5.1 Efficacy / Pharmacodynamics

Survival analysis

At the end of the treatment epoch, the Kaplan-Meier estimates of the proportion of patients with the event of interest, along with 80% two-sided confidence intervals using Greenwood's formula, will be provided. In addition, the Kaplan-Meier estimates will be plotted against time.

The two treatment groups will be compared using a one-sided logrank test at the 10% significance level. The hazard ratio and its associated 80% two-sided confidence intervals will be estimated.

Event of interest is defined as:

1. All-cause mortality
2. IPF-related mortality

Progression-free survival (PFS) analysis

Same survival analysis as defined above will be produced at the end of the treatment epoch for the following event of interest:

1. Events, defined as: death (all-cause mortality) **OR** "progression" (relative reduction in FVC $\geq 10\%$)
2. Events, defined as: death (IPF-related mortality) **OR** "progression" (relative reduction in FVC $\geq 10\%$)

Disease progression

At the end of the treatment epoch, the Kaplan-Meier estimates of the proportion of patients with progression, along with 80% two-sided confidence intervals using Greenwood's formula, will be provided. The two treatment groups will be compared using a one-sided logrank test at the 10% significance level. The hazard ratio and its associated 80% two-sided confidence intervals will be estimated.

1. Progression, defined as: relative reduction in FVC $\geq 10\%$
2. Progression, defined as: relative reduction in DLcO $\geq 15\%$
3. Progression, defined as: absolute reduction in 6MWD ≥ 50 m

Composite endpoint

At the end of the treatment epoch, the Kaplan-Meier estimates of the proportion of patients with event of interest, along with 80% two-sided confidence intervals using Greenwood's formula, will be provided, where events of interest is defined as below. The two treatment groups will be compared using a one-sided logrank test at the 10% significance level. The hazard ratio and its associated 80% two-sided confidence intervals will be estimated.

1. death (all-cause mortality), **OR** relative reduction in FVC $\geq 10\%$, **OR** relative reduction in DLcO $\geq 15\%$, **OR** relative reduction in 6MWD ≥ 50 m
2. death (IPF-related mortality), **OR** relative reduction in FVC $\geq 10\%$, **OR** relative reduction in DLcO $\geq 15\%$, **OR** relative reduction in 6MWD ≥ 50 m

Pulmonary physiology

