4.3 General definitions

Study treatment:

Study treatment will be noted as VAY736/Placebo throughout this document and CSR deliverables.

Study day:

The study day for safety/efficacy assessments (e.g. adverse event onset, laboratory abnormality occurrence, vital sign measurement, Electrocardiogram (ECG), PK sampling, FVC values, etc.,) will be calculated using the randomization date as the reference date. For assessments occurring: **on or after the randomization date**, the study day will be calculated as (date of assessment/occurrence) – (date of randomization) + 1. Then study day 1 will be the day of randomization.

before the randomization date, the study day will be calculated as (date of assessment/occurrence) – (date of randomization).

For example, if a serious adverse event starts 1 day before the randomization date, the study day displayed on the listing will be negative, i.e. -1.

Baseline:

For all evaluations, the last available pre-dose assessment before or on the date of randomization is taken as 'baseline' value or 'baseline' assessment.

Commercially Confidential Information

Unscheduled assessment:

There will be no analysis visit window defined, by consequence descriptive summary statistics by visit will not include unscheduled/repeat assessment.

For all analyses regarding abnormal assessments or analyses based on worst post-baseline value (e.g. laboratory, ECGs, vital signs), all post-baseline values will be included (scheduled, unscheduled, repeat). All unscheduled and repeat measurements will be included in listings.

Treatment analysis epoch:

Treatment epoch will be defined as any post-baseline assessment performed between the first dose of study drug date and the date of Week 49 visit if not missing or the date of last visit attended in treatment epoch (End of Study Treatment visit 199) in case of drop-out or the death date if subject died in treatment epoch.

Commercially Confidential Information

5 Statistical methods for Pharmacokinetic (PK) parameters

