6.2.1.4 Composite endpoint

Only events restricted to treatment epoch will be analyzed.

Time to composite events will be considered, where events of interest are defined as below:

- Death (all-cause mortality), OR relative reduction in FVC $\geq 10\%$, OR relative reduction in DLCO $\geq 15\%$, OR relative reduction in 6MWD ≥ 50 m;
- Death (IPF-related mortality), OR relative reduction in FVC $\geq 10\%$, OR relative reduction in DLCO $\geq 15\%$, OR relative reduction in 6MWD ≥ 50 m.

For the subjects who do not experience the events at the end of the treatment epoch, the time to event will be censored at the latest date of the FVC, DLCO or 6MWD assessments in the treatment epoch.

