6.2.3 Statistical model, assumptions and hypotheses

6.2.3.1 Time to Events analyses

CCI

The Kaplan-Meier estimates of the proportion of patients with the event of interest in each treatment group, along with 80 % two-sided confidence intervals using Greenwood's formula, will be provided. The two treatment groups will be compared using a one-sided log rank test at the 10% significance level. The hazard ratio and its associated 80% two-sided confidence interval will be estimated based on a Cox regression model using treatment group as main factor.

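### Time-to-progression endpoints: censoring each patient at their own last assessment date distorts the Kaplan-Meier proportion across the ±5-day Week 49 window, in a direction that depends on the day it is read

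*SAP*

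**What the plan says.** - **Censoring.** For the three disease-progression endpoints, SAP 6.2.1.3 states that "disease progression will be censored at the date of the last FVC, DLCO or 6MWD assessment in treatment epoch as applicable". For PFS1, SAP 6.2.1.2 states that "PFS will be censored at the date of last non-missing assessment of FVC"; PFS2 is similar, with an allowance for non-IPF death. For both composites, SAP 6.2.1.4 states that "the time to event will be censored at the latest date of the FVC, DLCO or 6MWD assessments in the treatment epoch". Seven secondary endpoints are covered.
- **Event time.** SAP 6.2.1.3: "Disease progression is defined as the time from randomization to progression". The visible text does not say which date counts as the date of progression.
- **Dating.** SAP 4.3 computes study day from the actual date: "date of assessment/occurrence) – (date of randomization) + 1". It adds: "There will be no analysis visit window defined". The treatment epoch ends at each patient's own Week 49 visit.
- **Visits.** Protocol 3.1 schedules efficacy assessments at Weeks 1, 13, 25, 37 and 49. Protocol Table 8-1 puts Week 49 at Day 337 ±5.
- **Estimate.** Protocol 11.5.1 asks for "At the end of the treatment epoch, the Kaplan-Meier estimates of the proportion of patients with progression", with 80% Greenwood intervals. SAP 6.2.3.1 has "The Kaplan-Meier estimates of the proportion of patients with the event of interest in each treatment group". No reading day appears in the visible text, but a redaction directly precedes that SAP sentence.

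**The concern.** Progression in FVC, DLCO or 6MWD can normally be seen only at four post-baseline visits. Among patients who reach Week 49, the exact day of attendance between Days 332 and 342 says nothing about when in the preceding 12 weeks they progressed. The Kaplan-Meier method nevertheless treats it as information. A patient seen on Day 333 without progression leaves the risk set, and a progression found on Day 341 is then divided by the few who have not yet attended. The natural denominator is everyone assessed at Week 49.

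At stake are the level and precision of the reported progression proportions for seven secondary endpoints. They would depend partly on who happened to attend late.

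**Working it through.** **Figure to reproduce.** None. The documents give no progression rate, event count or Kaplan-Meier proportion, so the rates below are assumptions.

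**Inputs from the documents.** 58 patients randomized 1:1 (Protocol 3.1), so 29 per arm; visits on Days 85, 169, 253 and 337, Week 49 within ±5 days (Table 8-1); censoring and dating as set out in SAP 4.3 and 6.2.1.2 to 6.2.1.4.

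**Assumptions.** Cumulative progression p by Week 49; equal risk per visit, h = 1 − (1 − p)^(1/4); events dated at the actual visit; attendance day unrelated to outcome; no deaths.

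**Step 1: one arm by hand.** Take p = 30%.

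- h = 1 − 0.7^0.25 = 0.085. Expected at risk at Week 49: 29 × 0.7^0.75 = 22.2. Expected Week 49 events: 22.2 × 0.085 = 1.9.
- So let 7 of 29 progress earlier, and let 22 attend Week 49, two on each of the 11 days, of whom 2 progress. The crude proportion is 9/29 = 31.0%.
- On nominal days: 1 − (22/29) × (20/22) = 31.0%.
- Progressions on Days 333 and 337 (20 and 12 at risk): 1 − (22/29) × (19/20) × (11/12) = 33.9%.
- Progressions on Days 337 and 341 (12 and 4 at risk): 1 − (22/29) × (11/12) × (3/4) = 47.8%.
- In the last case, read at Day 337: 1 − (22/29) × (11/12) = 30.5%, because the later event is not yet counted.

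The same 9 progressions in 29 patients give 33.9% or 47.8% at the end of the window, depending only on appointment dates.

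**Step 2: averages by simulation.** 8,000 trials per setting, 29 per arm, uniform ±5-day spread at every visit, no drop-out, events before censorings on tied days.

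| True p | End of window (Day 342) | Bias, points | Read at Day 337 | All on nominal days | Arm reaches 100% |
|---|---|---|---|---|---|
| 20% | 28% | +7.8 | 19% | 20% | 1.6% of trials |
| 30% | 41% | +10.8 | 28% | 30% | 2.9% |
| 40% | 52% | +12.4 | 38% | 40% | 4.7% |

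**Step 3: how far the size depends on assumptions (end of window).**

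- True rates 10% to 60%, uniform spread: +4.6 to +12.9 points.
- Triangular spread: +4.9 to +13.1. Half of visits exactly on the nominal day: +4.3 to +12.2.
- 20% drop-out, across the three spreads: +4.3 to +13.3.
- Share of all events that fall at Week 49, true rates 20% to 50%: a 10% share gives +3.7 to +7.6; 25%, +8.6 to +15.3; 40%, +12.8 to +21.0; 50%, +15.5 to +24.1.
- Read at Day 337 with uniform spread: −0.6 to −3.0 at equal risk per visit, and up to −8.5 if half the events fall at Week 49.
- On nominal days: within about ±0.2 points, with 0% or 20% drop-out.

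**Step 4: precision.** On nominal days without drop-out, each arm's SD is √[p(1 − p)/29] = 0.074, 0.085 and 0.091 for p = 20%, 30% and 40%. Simulated with actual dates and read at the end of the window, the SD of the between-arm difference is 0.23 to 0.24, so each arm's SD is about 0.23/√2 = 0.16 to 0.24/√2 = 0.17, roughly double.

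**Step 5: between-arm difference.** In a check of 4,000 trials with the same settings, the mean end-of-window difference was about 12 points for 20% v 30% (true 10), 12 for 30% v 40% (true 10) and 24 for 20% v 40% (true 20), and about zero for equal arms. Read at Day 337, the three unequal pairs gave 9, 10 and 19.

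**The case against.** The strongest reply is that the overstatement depends on a reading day that the visible text does not set. A 48-week epoch has its scheduled end visit at Day 337, and read there the error is a small understatement. The redaction ahead of the Kaplan-Meier sentence in SAP 6.2.3.1 may hide a stated day. This stands: neither the direction nor the size can be asserted from the documents alone. It does not clear the plan, because SAP 4.3 ends the epoch at each patient's own Week 49 visit, which is not a common day.

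Dating at the actual visit is also an inference. It is the natural one, since the study-day rule in SAP 4.3 names FVC values and no visible text moves them to nominal days.

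A reader might infer that the treatment comparison is biased by 8 to 12 points. The documents do not support that. If visit timing is alike in both arms, the log-rank test should stay valid under the null (reasoned, not simulated), and the mean bias in the difference is only about 2 to 4 points. What suffers is its precision.

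SAP 6.2.2 plans a list and summary of events, which will help a reader but does not correct the Kaplan-Meier estimate. The simulation has no deaths, so its figures carry over to PFS and the composites only as far as progression supplies the events. Finally, the trial is exploratory and its secondary endpoints are not powered, which limits the stakes.

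**Conclusion.** The concern holds in conditional form. Under the visible rules, the Kaplan-Meier progression proportion depends on appointment order within the last window.

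- Read at the end of the window, it is too high by about 8 to 12 points for assumed true rates of 20% to 40%, equal risk per visit and actual-visit dating, and by about 4 to 24 points over wider assumptions. Each arm's SD about doubles, and an arm occasionally reaches 100%.
- Read at Day 337, it is about 1 to 2 points too low for the same 20% to 40% rates.

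It would go too far to say that the plan overstates progression by a known amount, because the documents supply neither a progression rate nor a visible reading day. The point deserves correction because it affects seven secondary endpoints and the repair is cheap. It does not undermine the planned between-group test.

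**What to change.** In SAP 6.2.1.2 to 6.2.1.4:

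- Derive event and censoring times for scheduled Week 13, 25, 37 and 49 assessments at the nominal days (85, 169, 253, 337), with events before censorings on tied days. State explicitly that this is the progression date.
- Keep actual dates for deaths, and for early-termination or unscheduled assessments outside those visit windows, which have no nominal day.
- Count deaths inside the last window before the Day 337 censoring.

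In SAP 6.2.3.1, state that the Kaplan-Meier proportion is read at Day 337. If the redacted text already sets a day, reconcile it with this rule. Show number progressed over number assessed beside the estimate.

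The cost is a few lines of wording and one derived variable, with no new data. The small downside is more tied event times, which log-rank and Cox procedures handle.
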